6.3 Dose Modification

No dose adjustments during this study are planned for the DEC205mAb-NY-ESO-1 fusion protein (CDX-1401) given with adjuvant poly-ICLC vaccine.

In the event of excessive discomfort, skin breakdown or desquamation, or a Grade 3 treatment-related systemic toxicity following CDX-1401 and poly-ICLC dosing, administration of adjuvant (poly-ICLC) on the subsequent day should be omitted. Provided the toxicity has resolved to Grade 2 or less, the next monthly treatment may be administered as scheduled at a new administration site.

Refer to **Section 11.1** for the Phase I parameters and decisions rules for INCBO24360 dose adjustments.

Dose adjustments for hematological toxicity will be based on the blood counts obtained at baseline and after each 28-day cycle of DEC205mAb-NY-ESO-1 fusion protein (CDX-1401) given with adjuvant poly-ICLC and with or without INCBO24360.

If at least 2/3 or 2/6 DLT's are observed in cohort one, the dose of INCBO24360 will be reduced from 300 mg to 100 mg BID. If at least 2/3 or 2/6 DLT's are observed in Cohort 1, the dose of INCBO24360 will be reduced from 100 mg to 50 mg BID in Cohort 2. The study will continue at this dose level.

Dose modification for INCBO24360 are based on decision rules in **Section 11.1**.

Patients will be withdrawn from the study if they fail to recover to Grade 2, CTCAE Version 4.0, from a treatment-related toxicity within 4 weeks (leading to treatment delay of \geq 4 weeks. For patients that recover in $<$ 4 weeks, when toxicities have resolved to Grade 2 or lower, INCBO24360 may be restarted. In patients that recover from toxicity in less than 4 weeks and who restart therapy, the next treatment cycle will be scheduled for 4 weeks later. Additional cycles will also follow at 4 weeks intervals.

Dose modification for Phase IIB (INCBO24360 cohorts)

When an INCBO24360 toxicity is observed, dose administration may be delayed/interrupted to allow for recovery from toxicity. INCBO24360 may be restarted at a reduced dose of 100 mg. po BID. Please contact the PI for attribution.

Based on the phase I safety review, INCBO24360 300 mg. po BID x 7 cycles has been selected for the phase IIB dose. Dose modification criteria will be defined as any Grade 3 or higher treatment-related (i.e. definitely, probably, or possibly related) toxicity that occurs outside the DLT evaluation period including:

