6.3.1 Definition of Dose-Limiting Toxicity

Patients who do not complete the study through Day 29 for reasons other than dose limiting toxicities (DLTs) will be replaced. All patients will be included in the analysis results.

All AEs (as defined in **Section 9**) will be graded according to the NCI-CTCAE scale Version 4.0. Patients who experience a DLT will not receive any additional treatment (i.e., will be removed from the study and followed until resolution of their toxicity) and will not receive continued treatment even at a reduced dosage of the INCB024360 product. Patients with dose limiting toxicities requiring drug discontinuation (specified below) will be removed from the study (see exception for hypersensitivity reaction). The DLT period will be defined as 28 days after the first dose of vaccine. Late developing toxicities, occurring between Day 29 and Day 183 will be monitored throughout the study and according to the schedule of procedures and observations. Patients may be withdrawn from study even if DLT is due to INCB024360 or sirolimus alone. Safety monitoring will include careful assessment and appropriate reporting of AEs, as well as the construction and implementation of a data and safety-monitoring plan (Auditing, Monitoring, and Inspecting). Medical monitoring will include a regular assessment of the number and type of SAEs. Refer to the stopping rules for this study in **Section 6.3.2**. Any event(s) that might appear to trigger a treatment discontinuation rule or trial stopping rule will be discussed with the FDA review team. For phase IIb dose reductions for INCB024360 will be allowed (see section 6.3)

Management and dose modifications associated with AEs are outlined in **Section 6.3**. Refer to **Section 11** for statistical considerations and additional decision rules.

These events should be deemed to be possibly, probably or definitely related to study drugs. DLT criteria will be defined as any Grade 3 or higher treatment-related (i.e. definitely, probably, or possibly related) toxicity that occurs during the DLT evaluation period, including:

- Febrile neutropenia with standard of care treatment for ≥ 7 days. Growth factors may be used according to American Society of Clinical Oncology guidelines.
- Platelets $\leq 50 \times 10^9/L$
- Grade 3 or greater non-hematologic toxicity
- New onset pulmonary hypertension, interstitial pneumonitis or, CNS bleeding
- Serum bilirubin $> 3.0 \text{ mg/dL}$

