6.3.2 Management of Delayed Events

Late-developing toxicities, occurring between Day 29 and Day 143 will be monitored throughout the study and according to the schedule of procedures and observations.

Study Stopping Rules

Any Grade 4 event will trigger a study pause for data review prior to further enrollment. In addition, the following stopping rule for treatment-related SAEs will be used:

- Accrual to study will be suspended to allow protocol review with institutional IRB, the Early Phase Clinical Trials (EPCT) Committee, and the FDA review team if any of the following occurs among patients who receive experimental agents:
 - Any treatment-related death, judged to be possibly, probably, or definitely related to INCB024360 or DEC205mAb-NY-ESO-1 fusion protein (CDX-1401) given with adjuvant poly-ICLC.
 - Exploratory cohort at Roswell Park ONLY: Any treatment-related death, judged to be possibly, probably, or definitely related to sirolimus or DEC205mAb-NY-ESO-1 fusion protein (CDX-1401) given with adjuvant poly-ICLC.
 - Grade 4 events considered to be possibly, probably, or definitely related to the experimental agents.

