6.7 Treatment Discontinuation

Upon treatment discontinuation all end of study evaluations and tests will be conducted. All patients who discontinue due to an AE must be followed until the event resolves or stabilizes. Appropriate medical care should be provided until signs and symptoms have abated, stabilized, or until abnormal laboratory findings have returned to acceptable or pre-study limits. The final status of the AE will be reported in the patient's medical records and the appropriate eCRF. If patient terminates study participation prior to study completion, all efforts will be made to complete an early termination visit (within approximately 30 days of last dose). Assessment will include physical exam, vital signs and weight, performance status, labs (CBC/diff, CMP, LDH, Coag if on anticoagulants, con med/AE assessment.

Reasons for treatment discontinuation should be classified as follows:

- Death
- Progressive disease
- Treatment-related toxicity
 - Subjects who experience a DLT will not receive any additional treatment (i.e., will be removed from the study and followed until resolution of their toxicity) and will not receive continued treatment even at a reduced dosage of the INCB024360 product.
 - Persistent toxicity that is unresolved to a grade 2 toxicity, where subsequent treatment cannot be given.
- Toxicity unrelated to treatment
- Investigator judgment

- The Investigator may withdraw a patient if, in his/her judgment, it is in the patient's best interest to do so.
- Noncompliance
- Patient voluntary withdrawal
 - A patient may withdraw from the study at any time, for any reason. If a patient discontinues treatment, an attempt should be made to obtain information regarding the reason for withdrawal.
- Roswell Park's decision.

Patients who are unavailable for follow-up evaluations should be classified as lost to follow-up for 1 of the following reasons:

- Lost to follow-up: For a patient to be considered lost to follow-up, the Investigator must make 2 attempts to re-establish contact with the patient. The attempts to re-establish patient contact must be documented (e.g., certified letter).
- Death: Date and cause of death will be recorded for those patients who die within 30 days after last dose of study drug (telephone contact is acceptable).

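### INCB024360 cohorts: no safety labs scheduled between first dose and Cycle 2 Day 1, and the Phase IIb action for a DLT-level toxicity is unclear (for creatinine, in direct conflict)

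*Combined protocol and SAP*

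**What the plan says.** **Window.** Section 6.3.1 states: "The DLT period will be defined as 28 days after the first dose of vaccine". A DLT is a treatment-related Grade 3 or higher "toxicity that occurs during the DLT evaluation period". The same section replaces patients who leave before completing Day 29 for reasons other than a DLT, and it also starts the late period on that day: "Late developing toxicities, occurring between Day 29 and Day 183". Section 6.3.2 gives a different end: "Late-developing toxicities, occurring between Day 29 and Day 143".

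**Schedule.** Table 3 (INCB024360 cohorts) marks hematology and chemistry at Baseline and next at Cycle 2 Day 1. Section 6.3 bases hematological dose adjustment on counts at baseline and after each 28-day cycle. Table 4 (sirolimus cohort) also marks both rows at Cycle 1 Day 1 and Day 15. Section 7.7.1 has Cohort 2b giving PK blood on Cycle 1 Day 15.

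**Action.** Under 6.3.1 a patient with a DLT is removed and "will not receive continued treatment even at a reduced dosage of the INCB024360 product", with an exception for hypersensitivity. Section 6.7 repeats the rule without naming a phase: "Subjects who experience a DLT will not receive any additional treatment". Yet 6.3.1 also says "For phase IIb dose reductions for INCB024360 will be allowed (see section 6.3"). In 6.3, the Phase IIb block opens by saying that INCB024360 "may be restarted at a reduced dose of 100 mg. po BID" after an interruption, with no time window. It then limits its criteria to toxicity outside the DLT period. The creatinine item in that list is nevertheless labelled a DLT.

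**The concern.** Platelets, bilirubin, AST/ALT and creatinine can cross their limits without symptoms, so they are found by a blood test or not at all. If the first scheduled on-treatment test is at Cycle 2 Day 1, a Cohort 2b patient could pass a limit early in Cycle 1 and keep dosing. Scheduled data could not then date the onset, because the only earlier scheduled sample is Baseline.

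When the result does arrive, the site needs one instruction. AST/ALT above 3.5 x ULN is in both lists. Treated as a DLT it ends treatment; treated as a dose-modification event it permits a restart at 100 mg BID. At stake are patient safety and consistent management in Phase IIb.

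**Working it through.** The plan states no figure on this point, so the check is a count of table cells, day arithmetic, and a comparison of the rules.

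**1. Laboratory share of the criteria.** The list in 6.3.1 has eight items: febrile neutropenia, platelets, Grade 3 non-hematologic toxicity, the pulmonary and CNS events, bilirubin, AST/ALT, creatinine and hypersensitivity. Four are laboratory limits (platelets, bilirubin, AST/ALT, creatinine). The Phase IIb list in 6.3 drops the pulmonary and CNS item, which leaves seven, with the same four laboratory limits.

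**2. Table 3 columns.** Number the cells after Baseline as 1 = Cycle 1 Day 1, 2 = Cycle 1 Day 2, 3 = Cycle 1 Day 15, 4 = Cycle 2 Day 1.
- Hematology and chemistry: first mark at 4; cells 1 to 3 are empty.
- Vaccination: marks at 1, 4, 6, 8 and 10, which is Day 1 of Cycles 1 to 5, as the text requires.
- Disease assessment: first mark after Baseline at 8 = Cycle 4 Day 1, as in the synopsis.
- PK: marks at 1, 2 and 3. This does not match 7.7.1, which has no Day 2 sample and does have one at Cycle 2 Day 1.

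Two rows confirm the alignment and one does not. For blood counts, 6.3 independently supports the reading. For chemistry, which carries three of the four laboratory limits, the table stands alone.

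**3. Days.** Cycle 2 Day 1 = 1 + 28 = Day 29; with the 3-day allowance, Days 26 to 32. Baseline labs may be 28 days before first vaccination. The gap between consecutive scheduled labs is then up to 28 + 28 = 56 days at the nominal visit, or 28 + 31 = 59 at the latest. Scheduled draws after first dose and before Cycle 2 Day 1: 0 in Table 3 and 1 in Table 4 (Day 15).

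**4. Does the Cycle 2 Day 1 draw count?** Days 26 to 28 are inside the window. Day 29 can be read either way: the replacement rule treats it as part of the evaluable period, while the late-toxicity sentence treats it as late. Days 30 to 32 are outside on a literal reading. No sentence settles it.

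**5. Late-period end.** 183 - 143 = 40 days apart. Seven cycles end on Day 7 x 28 = 196, so the two limits fall 53 and 13 days before planned INCB024360 dosing ends. Routine AE reporting under 9.1.3 runs to 196 + 30 = Day 226.

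**6. The rules side by side, Phase IIb.**

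| Event | 6.3.1 and 6.7 | 6.3, Phase IIb block | Result |
|---|---|---|---|
| Listed toxicity inside the window | Removal, no reduced dose | Criteria do not reach it, but the restart sentence has no window and 6.3.1 points here for reductions | Unclear |
| Listed toxicity outside the window, other than creatinine (hypersensitivity has its own rule) | Not a DLT by definition | Restart at 100 mg BID allowed | Consistent |
| Creatinine Grade 3 or higher outside the window | Removal, because 6.3 labels it a DLT | Restart at 100 mg BID allowed | Conflict |

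**The case against.** The strongest reply is that the two rules divide by time: removal inside the DLT window, interruption and restart outside it. That reading is coherent for most criteria, so a reader who infers that the whole Phase IIb rule contradicts itself goes further than the text allows. What remains is narrower. The restart sentence has no window, the Phase IIb sentence in 6.3.1 reads like an exception to the bar on reduced doses, and 6.7 acknowledges no exception. The time split also fails for creatinine.

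A second reply is that Cycle 2 Day 1 labs can count toward Cycle 1, since 28 days after Day 1 is Day 29 and evaluability runs through Day 29. That is fair, and it reduces the window question to one clarifying sentence.

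A third is that other safeguards exist. Section 7.2 provides unscheduled visits for possibly related AEs, 11.5 promises weekly safety review including laboratory values, 6.3 refers attribution to the PI, and 6.3.1 sends events that might trigger a discontinuation or stopping rule to the FDA review team. None of these schedules a blood draw.

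A fourth is that the hepatic signal in section 1.6.2.4 (5 of 7 patients at 300 mg BID with ipilimumab) arose between 2 and 4 cycles, when monthly labs are already running, and that sirolimus has its own hematologic reasons for Day 15 labs. Both points stand. The signal shows that AST/ALT matters at this dose; it does not show that Cycle 1 onset is likely.

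**Conclusion.** The point holds in this form. As Table 3 reads, 25 Cohort 2b patients have no scheduled hematology or chemistry for about four weeks of 300 mg BID, with up to 59 days between consecutive scheduled labs. The action for an in-window Phase IIb DLT is unclear, and for creatinine of Grade 3 or higher outside the window it is contradictory as written. Confidence is good for hematology, because 6.3 agrees. It is moderate for chemistry, because the table text is partly damaged and the PK row does not match 7.7.1; the row should be checked against the typeset table.

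A reader might infer that Phase I missed DLTs and that the 300 mg BID choice is unsafe. The documents do not support that: dose selection is complete, nothing says Cycle 2 Day 1 results were left out, and no count of missed events is given. Nor is the PFS analysis touched; its definition does not depend on which action is taken, and patients who leave are to be followed for progression. The Day 143 and Day 183 mismatch loses no adverse events, since 9.1.3 still collects them.

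**What to change.** (a) State in 6.3.1 and 6.7 which rule governs a Cycle 1 INCB024360 toxicity in Phase IIb: interruption with restart at 100 mg BID or, if intended, removal. Delete the words in the Phase IIb creatinine item of 6.3 that make it a DLT. Cost: wording only.

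(b) In Table 3, add hematology and chemistry at Cycle 1 Day 15 for Cohort 2b. Cost: one cell in each of two rows, and one routine sample per patient at a visit already attended for PK. The downside is unequal ascertainment: laboratory abnormalities would be sought mid-cycle in one arm of an open-label comparison. Keep abnormalities found only at that draw out of any between-arm AE comparison, or sample Cohort 2a as well, at up to 25 extra visits.

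(c) As minor wording, say that pre-dose Cycle 2 Day 1 labs count toward the Cycle 1 assessment on whichever permitted day they are drawn. This extends the window by at most 32 - 29 = 3 or 32 - 28 = 4 days, depending on where it now ends. Give one late-toxicity end day in 6.3.1 and 6.3.2, for example 30 days after the last study-drug dose, in line with 9.1.3.

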6.3.2 Management of Delayed Events

Late-developing toxicities, occurring between Day 29 and Day 143 will be monitored throughout the study and according to the schedule of procedures and observations.

Study Stopping Rules

Any Grade 4 event will trigger a study pause for data review prior to further enrollment. In addition, the following stopping rule for treatment-related SAEs will be used:

- Accrual to study will be suspended to allow protocol review with institutional IRB, the Early Phase Clinical Trials (EPCT) Committee, and the FDA review team if any of the following occurs among patients who receive experimental agents:
 - Any treatment-related death, judged to be possibly, probably, or definitely related to INCB024360 or DEC205mAb-NY-ESO-1 fusion protein (CDX-1401) given with adjuvant poly-ICLC.
 - Exploratory cohort at Roswell Park ONLY: Any treatment-related death, judged to be possibly, probably, or definitely related to sirolimus or DEC205mAb-NY-ESO-1 fusion protein (CDX-1401) given with adjuvant poly-ICLC.
 - Grade 4 events considered to be possibly, probably, or definitely related to the experimental agents.

6.4 Ancillary Therapy and Supportive Care

Patients may not receive chronic treatment during the period of study with systemic corticosteroids or other immunosuppressive agents including chemotherapeutic agents. A brief course of systemic corticosteroids can be used to manage immune based toxicities, if deemed appropriate by the treating physician. Treatment with NSAIDs should be avoided during the study. Investigators may prescribe all other concomitant medications or treatments deemed necessary to provide adequate patient care.

Concurrent non-cytotoxic anti-cancer therapy (e.g., hormone therapy) is permitted.

The electronic case report form (eCRF) must capture the concurrent use of all other drugs, over-the-counter medications, or alternative therapies, listing drug name, indication, dose, route of administration, and dates of administration.

Patients may be pretreated for nausea and vomiting with appropriate anti-emetics.

6.4.1 Permitted Treatment

- Any medication for concurrent medical condition.
- Inhaled corticosteroids, if indicated.
- If clinically indicated, use of growth factors according to American Society of Clinical Oncology guidelines.
- Antiemetics for breakthrough nausea and vomiting:

- Metoclopramide 1 mg - 2 mg/kg IV every 3 to 4 hours p.r.n. nausea/vomiting.
- Prochlorperazine 10 mg IV/PO every 4 to 6 hours p.r.n. nausea/vomiting.
- Lorazepam 0.5 mg - 2 mg PO/SL/IV every 4 to 6 hours p.r.n nausea/vomiting.
- Olanzepine 2.5 mg - 5 mg PO twice daily.
- Use of coumarin-based anticoagulants (e.g. Coumadin) is discouraged. Low-dose coumadin (1 mg) is acceptable; however, doses that increase the INR are discouraged and will require dose modification. If an alternative to coumarin-based anticoagulants cannot be used, dose adjustment of the Coumadin may be needed. Based on the observed magnitude of epacadostat/warfarin PK interaction and PK/PD modeling results, for an epacadostat dose of 300 mg BID, the dose of warfarin should be reduced by approximately one-third after initiation of epacadostat administration based on approximately 30% to 40% reduction in S- and R-warfarin oral clearance values. Close INR monitoring is recommended for patients on a stable dose of warfarin who are starting treatment with epacadostat. Based on PK/PD modeling, recommendations for warfarin dose modifications for subjects receiving other epacadostat doses, are summarized below based on the INR prior to starting epacadostat.

Stable Baseline INR	Epacadostat Dose		
INR \leq 2.5	≤ 100 mg BID Close INR monitoring	200 mg BID Close INR monitoring	300 mg BID Reduce warfarin by~33% and monitor INR
INR >2.5	Close INR monitoring	Reduce warfarin by 20-25%/monitor INR	Reduce warfarin by ~33%/monitor INR

6.5 Prohibited Treatment

Chemotherapy, radiation, surgery, immunosuppressive therapies are prohibited throughout this study. Patients being treated with a monoamine oxidase inhibitor (MAOI), or drug which has significant MAOI activity (e.g., meperidine, linezolid, methylene blue) within 3 weeks prior to screening is prohibited. Patients who are currently receiving therapy with a potent CYP3A4 inducer or inhibitor is prohibited. Use of UGT1A9 inhibitor including: diclofenac, imipramine, and ketoconazole is prohibited. Inhaled corticosteroids or short course of systemic corticosteroids are permitted. Daily nonsteroidal anti-inflammatory drugs for more than 2 weeks are not permitted.

Sirolimus Exploratory Cohort: At the investigator's discretion full dose anti-coagulation therapy may need to be adjusted for study procedures. Daily nonsteroidal anti-inflammatory drugs for more than 2 weeks are not permitted. The use of posaconazole and voriconazole are contraindicated because of drug-drug interactions. An additional list of drugs that have theoretical or probable interaction with sirolimus is provided in Appendix B. Patients taking any of these drugs will be

monitored clinically. Treatment with corticosteroids should be avoided during this study. However, a short duration (≤ 2 weeks) with systemic corticosteroids will be allowed for treatment of acute events.

6.6 Duration of Treatment

The duration of patient enrollment is expected to be 8 years.

INCB groups: Patients are expected to participate in the study for approximately 28 weeks of active therapy and follow-up assessments at 3 months, 6 months, and 12 months after the last dose of study drug. Patients may return to standard of care after completing all assessments at follow-up.

Exploratory Cohort with Sirolimus: Patients are expected to participate in the study for approximately 20 weeks of active vaccine therapy and follow-up assessments at 3 months, 6 months and 12 months after the last dose of study drug. Patients may return to standard of care after completing all assessments at End of Treatment.

6.7 Treatment Discontinuation

Upon treatment discontinuation all end of study evaluations and tests will be conducted. All patients who discontinue due to an AE must be followed until the event resolves or stabilizes. Appropriate medical care should be provided until signs and symptoms have abated, stabilized, or until abnormal laboratory findings have returned to acceptable or pre-study limits. The final status of the AE will be reported in the patient's medical records and the appropriate eCRF. If patient terminates study participation prior to study completion, all efforts will be made to complete an early termination visit (within approximately 30 days of last dose). Assessment will include physical exam, vital signs and weight, performance status, labs (CBC/diff, CMP, LDH, Coag if on anticoagulants, con med/AE assessment.

Reasons for treatment discontinuation should be classified as follows:

- Death
- Progressive disease
- Treatment-related toxicity
 - Subjects who experience a DLT will not receive any additional treatment (i.e., will be removed from the study and followed until resolution of their toxicity) and will not receive continued treatment even at a reduced dosage of the INCB024360 product.
 - Persistent toxicity that is unresolved to a grade 2 toxicity, where subsequent treatment cannot be given.
- Toxicity unrelated to treatment
- Investigator judgment

- The Investigator may withdraw a patient if, in his/her judgment, it is in the patient's best interest to do so.
- Noncompliance
- Patient voluntary withdrawal
 - A patient may withdraw from the study at any time, for any reason. If a patient discontinues treatment, an attempt should be made to obtain information regarding the reason for withdrawal.
- Roswell Park's decision.

Patients who are unavailable for follow-up evaluations should be classified as lost to follow-up for 1 of the following reasons:

- Lost to follow-up: For a patient to be considered lost to follow-up, the Investigator must make 2 attempts to re-establish contact with the patient. The attempts to re-establish patient contact must be documented (e.g., certified letter).
- Death: Date and cause of death will be recorded for those patients who die within 30 days after last dose of study drug (telephone contact is acceptable).

